
6.1.1 Baseline

Demographic characteristics, including age, body weight, height, BMI and race will be presented for all infused subjects, in the form of summary statistics. Other baseline characteristics, including previous treatment characteristics, disease history, previous number of bleeds, laboratory findings and vital signs, will be handled similarly.

6.1.2 Extent of exposure

Extent of exposure to the study drug, including infusion characteristics, will be summarized for each subject receiving any amount of drug. In addition, extent of exposure for surgeries will be summarized separately.

6.2 Efficacy

All subjects receiving study drug who have infusion/bleeding data from the EPD will be included in the efficacy analysis. The primary efficacy variables will be the annualized number of total bleeds (sum of spontaneous bleeds, trauma bleeds, and untreated bleeds) that occur within 48 hours after all prophylaxis infusions. Also summarized will be annualized number of joint bleeds, spontaneous bleeds, and trauma bleeds that occur within 48 hours after all prophylaxis infusions. Additional variables summarized will be annualized number of total bleeds, joint bleeds, spontaneous bleeds, and trauma bleeds. Other variables summarized will be the number of treatments required to control all bleeds and the subject's assessment of the response to treatment of all bleeds (poor, moderate, good, or excellent).

All efficacy variables will be summarized using the ITT analysis set. The primary efficacy variable will also be summarized using the PPS.

For subjects undergoing surgery (both major and minor), FVIII levels from the day prior to surgery through the post-operative period will be summarized by timepoint and listed. Study drug and blood product infusions will also be summarized and listed for these subjects, as well as blood loss at surgery and the assessment of hemostasis during the perioperative period by both the surgeon and the investigator.

Factor VIII concentration values and recovery values will be summarized by time point.

recovery = (post-infusion FVIII – pre-infusion FVIII) * weight / dose (in IU)

If a Factor VIII concentration value is below the LLOQ (lower limit of quantification), a data point will be substituted by one half of this limit.

A validity flag for recovery values and their corresponding pre- and post-infusion FVIII values will be created. These values will be considered valid except when any of the following conditions apply:

- If pre-infusion FVIII >= post-infusion FVIII [biologically impossible in the absence of inhibitors]
- If pre-infusion FVIII > 40 IU/dl (note 1 IU/dl=1%) [protocol violation]

In the tables displaying descriptive statistics of recovery values, if a recovery is flagged as not valid, then the corresponding pre-infusion FVIII, post-infusion FVIII, and recovery values will not be included.

Each subject's last FVIII trough value (pre-infusion value) will be summarized by time interval within 48 = -6 hours, 60 + -6 hours, 72 + -6 hours, 84 + -6, >=90 hours, and >36 hours after previous infusion will be summarized. Mean trough level >36 hours after last infusion will be calculated for correlations.

Spearman Correlations will be provided for the following:

• annualized bleeds and mean FVIII trough value (pre-infusion)

- annualized joint bleeds and mean FVIII trough value (pre-infusion)
- time to bleed treatment and bleed severity
- *#* of infusions to treat bleed and bleed severity
- first dose to treat bleed (IU/kg) and bleed severity
- time to bleed treatment and response to treatment of the bleed
- # of infusions to treat bleed and response to treatment of the bleed
- first dose to treat bleed (IU/kg) and response to treatment of the bleed

6.2.1 Required variables in efficacy data sets:

The following variables are needed in the efficacy data sets.

The sequence for derivation of these 3 data sets is: Infusion, bleed, and subject.

Subject level dataset:

One record per subject:

indicator variable: prophylaxis treatment regimen ($\leq 2x$ /week or $\geq 2x$ /week) [see formula for number of prophylaxis infusions per week in Section 4.5]

prophylaxis dose (15-50 IU/kg)

indicator variable: weekly prophylaxis dose (<80 IU/kg, >=80 IU/kg)

indicator variable: prior treatment (prophylaxis, on-demand)

indicator variable: target joint (no/yes)

number of target joints

number of days in study [last day in study – 1st day in study + 1]

total bleeds (spontaneous/trauma/untreated/'other')

total bleeds (spontaneous/trauma/untreated/'other') within 48 hours after prophylaxis infusions

joint bleeds

joint bleeds within 48 hours after prophylaxis infusions

spontaneous bleeds

spontaneous bleeds within 48 hours after prophylaxis infusions

trauma bleeds

trauma bleeds within 48 hours after prophylaxis infusions

total bleeds per year

total bleeds within 48 hours after all prophylaxis infusions per year

joint bleeds per year

joint bleeds within 48 hours after all prophylaxis infusions per year

spontaneous bleeds per year

spontaneous bleeds within 48 hours after prophylaxis infusions per year

trauma bleeds per year

trauma bleeds within 48 hours after prophylaxis infusions per year

'other' bleeds # untreated bleeds if subject has a target joint, % of joint bleeds in target joint exposure days [number of different calendar days with at least one infusion] number of infusions/subject total dose (IU) total dose per kg (IU/kg) total dose per kg per year (IU/kg/year) dose per infusion (IU/kg/infusion) total dose per infusion (IU/infusion) total dose per year (IU/year). number of prophylaxis infusions/subject total dose for prophylaxis (IU) total dose for prophylaxis per kg (IU/kg) prophylaxis dose per year (IU/kg/year) dose per prophylaxis infusion (IU/kg/infusion) total prophylaxis dose per infusion (IU/infusion) total prophylaxis dose per year (IU/year) number of infusions for bleeds Total dose for bleeds (IU) Total dose per bleed (IU/bleed) First dose per bleed (IU/kg/bleed) Total dose per kg for bleeds (IU/kg) Total dose per kg per bleed (IU/kg/bleed) Total dose per kg per spontaneous bleed (IU/kg/bleed) Total dose per kg per trauma bleed (IU/kg/bleed) Total dose per year for bleeds (IU/year) Total dose per infusion for bleeds (IU/inf) Dose per infusion for bleeds (IU/kg/inf) Dose per year for bleeds (IU/kg/year) number of infusions for surgery Total surgery dose (IU) Total surgery dose per kg (IU/kg) Total surgery dose per infusion (IU/inf) Dose per surgery infusion (IU/kg/inf) **Bleed level dataset (ADCE):** One record per bleed per subject:

indicator variable: bleed treated (no/yes) indicator 1st bleed since most recent prophylaxis infusion (no/yes) number of infusions number of infusions (0, 1, 2, 3, 4, >4) number of infusions (<=2, >2) **Statistical Analysis Plan**

reason for 1st infusion (spontaneous, trauma, other, missing) type of bleed (joint, muscle, skin/mucosa, internal, other) if joint bleed and subject has a target joint,

indicator variable: bleed in target joint or bleed not in target joint response to treatment (poor, moderate, good, excellent) bleed severity (mild, moderate, severe) time from this bleed to 1st infusion for this bleed (hours) time from last prophylaxis infusion to this bleed (days) time from last prophylaxis infusion to this bleed (<1, 1-2, 2-3, 3-4, 4+ days) indicator variable: bleed within 48 hours after most recent prophylaxis infusion time from last infusion to this bleed (days)

Infusion level dataset (ADEX):

One record per infusion per subject:

indicator variable: drug used was study drug (no/yes)

indicator variable: in reason for infusion was prophylaxis, was there a bleed within 48 hours (no/yes)

reason for infusion (prophylaxis (including additional prophylaxis), spontaneous-1st infusion, trauma-1st infusion, surgery, follow-up, other)

dose (IU)

most recent body weight

dose (IU/kg) [use most recent body weight]

time from last infusion to this infusion (days)

time of day [morning, (06:00 - 13:59), afternoon (14:00 - 21:59), night (22:00 - 5:59)] time from last prophylaxis infusion to this infusion (days)

An example for infusion/bleed/subject data is shown below. The subject has 182 days in study with 52 exposure days and total bleeds equal 2:

Infusions data set (ADXB)	Bleeds data set (ADXC)	Subject data set (ADXA)
Infusion #/reason	# of infusions per bleed/type	# of bleeds/

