7.3.2.2 Treatment logs / bleeding verification

Treatment (as of Amd 1) logs are commonly used for hemophilia subjects for documentation of their home treatment. Home treatment and bleeding frequency are key variables evaluated in this study. Study specific logs will be provided in national language. The preferred system for this study will be EPD devices since they are interactive, allow for real time data transmission, record-stamp date and time of fulfillment and facilitate the clarification of data with the site and also the data cleaning process.

Subjects/parents/caregivers will be provided with EPDs for the whole study. At Screening and Baseline visits, subjects and parents/caregivers will be trained in the use of the device. These logs will be used to collect the *treatment (as of Amd 1)* data and bleeding episodes by the parents/caregivers or subjects, and interact on a *regularly scheduled (as of Amd 1)* basis with the investigator or delegate to verify and complete the *data on (as of Amd 1)* the EPD. Thus, the EPD will be considered the source for these data.

For each *use* of study medication including the *infusions* administered during a planned visit for evaluation of recovery, information must be recorded on the *Treatment (as of Amd 1)*

Logs as follows:

1. Date and time
2. Lot numbers / number of vials administered

3. Reason for *treatment (as of Amd 1)* (prophylaxis, spontaneous bleed first treatment, trauma bleed first treatment, follow-up treatment, surgery, other). ***(If an infusion is given in response to a fall or identified trauma, such as may occur when a child has an uncomplicated blow to the head and there is no clinical sign or evidence of bleeding, the event should be recorded as prophylaxis.) (as of Amd 1)***

If treatment is for a bleeding episode: site of bleeding, severity (severe, moderate, mild), and response to treatment (excellent, good, moderate, *poor, too early to tell*) ***are to be recorded. If 'too early to tell' is entered, the subject will be queried for a response the next time they use the device. For guidance to the subject or their caregivers, the following definitions for response to treatment are suggested. Individual subject responses may vary (as of Amd 1):***

- ***Excellent: Abrupt pain relief and /or improvement in signs of bleeding with no additional infusion administered (as of Amd 1)***

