- ***Good: Definite pain relief and/or improvement in signs of bleeding, but possibly requiring more than one infusion for complete resolution (as of Amd 1)***
- ***Moderate: Probable or slight improvement in signs of bleeding, with at least one additional infusion for complete resolution (as of Amd 1)***
- ***Poor: No improvement at all between infusions or condition worsens. (as of Amd 1)***

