4.1 General Principles

The statistical evaluation will be performed by using the software package SAS release 9.2 or higher (SAS Institute Inc., Cary, North Carolina, United States). All data will be listed and summary tables will be provided. The number of data available and missing data, mean, standard deviation, and other summary statistics will be calculated for continuous data. Frequency tables will be generated for categorical data. Unless otherwise noted, any statistical tests will be 2-sided and performed at the 0.05 significance level.

Standard programs such as ADMAP and MOSTO will be used.

There will be a Validity Review Meeting and it is possible that this SAP might be updated based on the Validity Review Report.

The primary variable is the annualized number of total bleeds (sum of spontaneous bleeds, trauma bleeds, untreated bleeds, and 'other' bleeds) that occur within 48 hours after all prophylaxis infusions. [Note this is a change from the protocol that defined total bleeds to be the sum of spontaneous bleeds and trauma bleeds.]

Secondary efficacy parameters are:

- Annualized number of total bleeds (sum of spontaneous bleeds, trauma bleeds, untreated bleeds, and 'other' bleeds) during prophylaxis treatment
- Hemostatic outcome of surgeries (both major and minor) including blood loss, transfusion, and/or hemostatic-related surgical complications
- FVIII recovery values
 [note: recovery = (post-infusion FVIII pre-infusion FVIII) * body weight / IU]

Additional efficacy parameters are:

- Annualized number of joint bleeds, spontaneous bleeds, and trauma bleeds that occur within 48 hours after all prophylaxis infusions
- Annualized number of joint bleeds, spontaneous bleeds, and trauma bleeds

- % of joint bleeds in target joint for subjects with target joint
- Number of infusions for the treatment of bleeds per bleed
- For all infusions and prophylaxis infusions, FVIII usage calculation expressed in number of infusions, IU, IU/kg, IU/infusion, IU/year, IU/kg/infusion, and IU/kg/year.
- For bleed infusions, FVIII usage calculation expressed in number of infusions, IU, IU/bleed, IU/kg/bleed, IU/bleed (first infusion), IU/kg/bleed (first infusion), IU/infusion, IU/year, IU/kg/infusion, and IU/kg/year.
- For surgery infusions, FVIII usage calculation expressed in number of infusions, IU, IU/kg, IU/infusion, and IU/kg/infusion.
- Description of bleeding according to type, severity, and location as indicated on EPD

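### Part A plans six bleed-level Spearman correlations with no allowance for several bleeds per child, and the infusions-versus-response pair is partly circular

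*SAP*

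**What the plan says.** Section 6.2 of the Part A SAP introduces its list with "Spearman Correlations will be provided for the following" and names eight pairs. Two relate a child's annualized bleeds, or joint bleeds, to his mean trough level, so each child supplies one value. The other six relate time to treatment, number of infusions, or first dose to either bleed severity or response. One of these pairs the number "of infusions to treat bleed and response to treatment of the bleed".

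Section 6.2.1 describes the bleed data set as "One record per bleed per subject" and places severity, response, number of infusions and time to first infusion there. First dose can be read from the infusion records, but both of its partners are bleed-level, so those two pairs are bleed-level as well. The SAP states no unit of analysis, cluster adjustment or one-bleed-per-child rule for these correlations. The July 2013 supplement does not mention them.

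On testing, SAP section 4.1 says that, unless otherwise noted, "any statistical tests will be 2-sided and performed at the 0.05 significance level". Protocol section 8.4 says there will be no formal tests.

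Protocol section 7.3.2.2 offers caregivers suggested response definitions. *Excellent* includes "improvement in signs of bleeding with no additional infusion administered". *Moderate* is a slight or probable improvement "with at least one additional infusion for complete resolution". *Good* allows one infusion or more. *Poor* carries no count.

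**The concern.** Bleeds from one child are likely to resemble each other. Protocol section 6.1.2 leaves the bleed dose to the investigator, and section 7.3.1 makes the response rating the subject's or parents' own. A child with many bleeds then brings less information than his record count suggests. The standard p-value or interval for a Spearman coefficient assumes independent records, so it would overstate the evidence.

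The second problem concerns one pair only. If a rater follows the guidance, a bleed that needed a second infusion cannot be *excellent*, and a bleed that needed only one cannot be *moderate*. Part of the correlation between infusions and response then reflects the wording of the scale and says nothing about the bleed.

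At stake is the reading of exploratory results. No decision rule in the plan uses them.

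**Working it through.** The documents give no bleed count, within-child correlation (ICC), response distribution or expected rho. There is no figure of the plan's own to reproduce, and every input below other than the 50 children in A is an assumption.

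**Clustering.** If two unrelated variables each have within-child correlation ICC, the variance of the correlation is inflated by roughly

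1 + (m* - 1) × ICC², where m* = Σn² / Σn and n is the number of bleeds per child.

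Inflation therefore needs similarity in both variables and grows when a few children supply many bleeds. Two examples:
- Two bleeds in every child, ICC 0.2: 1 + (2 - 1) × 0.04 = 1.04.
- Mean of four bleeds, very uneven counts (m* = 10.6), ICC 0.6: 1 + 9.6 × 0.36 = 4.46.

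The formula applies to uncategorised variables. Simulation with ordinal variables gives smaller ratios.

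Setting A: 50 children (SAP section 3.1), both variables ordinal, true rho 0, naive two-sided 0.05 test, 4,000 runs per cell. Uneven counts are gamma-Poisson with variance = mean + 1.5 × mean². The Monte Carlo standard error near 5% is √(0.05 × 0.95 / 4000) = 0.3 percentage points.

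| Bleeds per child | ICC 0 | 0.2 | 0.4 | 0.6 |
|---|---|---|---|---|
| 2, equal | 5.0% | 5.8% | 5.8% | 7.4% |
| mean 2, uneven | 4.6% | 6.4% | 8.8% | 14.9% |
| 4, equal | 5.2% | 5.9% | 7.6% | 12.2% |
| mean 4, uneven | 4.8% | 6.3% | 13.5% | 23.6% |

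As a check, the simulated variance ratio in the bottom right cell was 2.71. A nominal 5% test then rejects with probability P(|Z| > 1.96 / √2.71) = P(|Z| > 1.19) = 0.234, which agrees with 23.6%.

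Setting B: 35 children, gamma-Poisson counts with mean 4 and shape 1, 3,000 runs per ICC. The expected total is 35 × 4 = 140 bleeds. The chance of no bleed is 1 / (1 + 4) = 20%, so about 35 × 0.8 = 28 children contribute. Rejection was 5.4%, 11.5%, 20.6% and 31.7% at ICC 0, 0.3, 0.5 and 0.7. These figures correspond to variables left continuous. Cutting both into a few categories, as in A, lowers them, so 31.7% is the upper end.

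Across both settings, rejection with any within-child correlation runs from 5.8% to 31.7%. With none it stays at 4.6% to 5.4%.

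**Overlap of infusions and response.** Draw a clinical impression independently of the number of infusions: *poor* 10%, *moderate* 20%, *good* 40%, *excellent* 30%. Then apply only the count clauses: *excellent* with an extra infusion becomes *good*, and *moderate* without one becomes *good*. Spearman rho, with response coded from *poor* up to *excellent* (200,000 bleeds):

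| Share of bleeds with one infusion | Clauses ignored | Followed half the time | Always followed |
|---|---|---|---|
| 60% | 0.00 | -0.16 | -0.38 |
| 70% | 0.00 | -0.15 | -0.35 |
| 80% | 0.00 | -0.13 | -0.31 |
| 90% | 0.00 | -0.10 | -0.23 |

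The true association is zero in every cell.

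**The case against.** The strongest reply is that the plan calls for no test here. Section 6.2 says only that correlations will be provided, the 0.05 level in section 4.1 is a default for tests that are run, and protocol section 8.4 rules out formal tests. A descriptive rho does not need independent records. This stands. A reader might infer that the SAP declares bleeds independent or plans these p-values, and it does neither. What remains is that the two documents leave open whether p-values or intervals will appear. The table specifications and analysis-dataset documents, which SAP section 1 makes part of the plan, may settle it but are not available here.

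A reader might also infer that response is simply defined by infusion count, so that the pair would show an association whatever the drug does. The protocol does not support that. Each category rests first on the clinical course, *good* permits any count, *poor* has none, and the definitions are suggestions from which individual ratings may vary. If raters ignore the count clauses, the artefact is about zero.

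Third, the documents do not say that a few children supply most bleeds or that ratings are caregiver habit. Both are plausible assumptions. The 24-hour and 72-hour rules in SAP section 4.5 merge some closely spaced bleeds, but they still leave several records per child.

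Finally, these correlations are not among the primary, secondary or additional efficacy parameters in section 4.1, and the Part B SAP lists none of them. This limits the importance of the point without answering it.

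**Conclusion.** The point holds in a limited form. Six of the eight correlations are bleed-level and make no allowance for repeated bleeds in a child. The two trough correlations are not affected. The six coefficients can stand as description, with more weight falling on frequent bleeders. A naive p-value or interval beside them would be too certain by an unknown amount: inflation is slight if counts are even and within-child correlation is low, and substantial if counts are skewed and correlation is high. The range of about 6% to 32% rests wholly on assumed counts and correlations.

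The infusions-versus-response pair is partly circular. The size of the artefact, a rho of about -0.4 to 0, depends on rater adherence and on the assumed response mix, so an observed value in that range could not be attributed to the clinical course of the bleeds. The matter is minor and exploratory.

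**What to change.** For the bleed-level pairs, state the unit of analysis, report the coefficient with a 95% interval from a bootstrap that resamples children with all their bleeds, and print no naive p-values. Drop the infusions-versus-response pair, or keep it with an explicit note that the two variables overlap by definition.

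Section 1 of the Part B SAP says the Part A analysis is complete and reported. The change is therefore a short re-analysis or a reporting caveat, to be carried into the overall analysis in protocol section 8.5 if these correlations are repeated there. The cost is a little programming and wider intervals. No new data are needed.

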		# of joint bleeds/
		# of spontaneous bleeds/
		# bleeds per year
1/prophy		
2/bleed	1/joint	2/1/1/(2*365.25/182)
3/prophy		
4/ bleed	2/muscle	
5/follow-up		
Etc		

Statistical Analysis Plan

BAY 81-8973 / 13400

52/prophy	

If subjects are treated with non-study FVIII drug, we may repeat the efficacy analysis combining non-study FVIII drug with study drug in bleeds/infusions. Alternatively, we may list these subjects, depending on the number of such cases we observe in the study. If we decide to repeat the efficacy analysis for combined study drug FVIII and non-study drug then corresponding variables will be derived.

6.3 **Pharmacokinetics / pharmacodynamics**

The concentration-times courses of FVIII will be tabulated for the planned sampling points at pre-infusion, 20-30 minutes, 4 hours (range approximately 3-5 hours for summary statistics), and 24 hours (range approximately 22-26 hours for summary statistics) after the end of infusion. The following statistics will be calculated for each of the sampling points (if appropriate): geometric mean, geometric standard deviation (re-transformed standard deviation of the logarithms) and coefficient of variation, arithmetic mean, standard deviation and coefficient of variation, minimum, median, maximum value, and the number of measurements.

Pharmacokinetic characteristics will be summarized by the statistics mentioned above.

Individual and mean (if appropriate) concentration vs time profiles (using the actual sampling times for individual plots and the planned sampling times for mean plots) will be plotted using both linear and semilogarithmic scale. Incremental recovery will be calculated taking the baseline value into account.

Pharmacokinetic parameters, as well as FVIII levels, will be displayed in subject listings.

